2.1.3.10 Visit remapping and assessment windows

If a scheduled visit did not occur, the data from the treatment discontinuation or study discontinuation visit may be used as the data from the scheduled visit, if the treatment discontinuation or study discontinuation visit occurred closer to the planned study day of the missing scheduled visit than to the planned study day of any other scheduled visit. In this case the treatment discontinuation or study discontinuation visit will be treated as the scheduled visit for the purpose of all analyses so that no missing data imputation will be necessary. Otherwise the data from any scheduled visit that did not occur will be dealt with like any other missing data. If the treatment discontinuation or study discontinuation visit is not re-mapped to any scheduled visit, it will be treated as an unscheduled visit that does not appear in by-visit summaries.

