## **8 Visit schedule and assessments**

Assessment schedule lists all of the assessments and indicates with an "X" or an "S", the visits when they are performed. All data obtained from these assessments must be supported in the patient's source documentation with those events marked by an "X" being captured in the CRF/Clinical Database and those marked with an "S" will be captured in source documentation only.

Patients should be seen for all visits/assessments as outlined in the assessment schedule or as close to the designated day/time as possible. Missed or rescheduled visits should not lead to automatic discontinuation. Patients who prematurely discontinue the study for any reason should be scheduled for a visit as soon as possible, at which time all of the assessments listed for the final visit will be performed. At this final visit, all dispensed investigational product should be reconciled, and the adverse event and concomitant medications recorded on the CRF.

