- If a patient undergoes nasal surgery, including but not limited to the following: treatment of nasal polyposis, septal deviation correction, turbinectomy, para-nasal sinus drainage, nasal plastic surgery, hypophysis tumor nasal approach.
- If a patient develops a medical condition, that requires consistent use of prohibited treatment as per [Section 6.2.2](#) or if patient exhibits a behavior of non-compliance regarding prohibited medication.

If discontinuation of study treatment occurs, the Investigator should make a reasonable effort to understand the primary reason for the subject's premature discontinuation of study treatment and record this information.

[figure not shown]
Subjects who discontinue study treatment or who decide they do not wish to participate in the study further should NOT be considered withdrawn from the study UNLESS they withdraw their consent (see withdraw of informed consent section.). **Where possible, they should return for the assessments indicated** in the Assessment schedule ( [Table 8-1](#) ).

After study treatment discontinuation, at a minimum, in abbreviated visits, the following data should to be collected at clinic visits or via telephone visits:

- new/concomitant treatments including OCS use
- adverse events/Serious Adverse Events

If they fail to return for these assessments for unknown reasons, every effort (e.g. telephone, e-mail or letter) should be made to contact the subject/pre-designated contact as specified in the lost to follow-up section. This contact should preferably be done according to the study visit schedule.

If the patient cannot or is unwilling to attend any visit(s), the site staff should maintain regular telephone contact with the patient, or with a person pre-designated by the patient. This telephone contact should preferably be done according to the study visit schedule. The information already collected during the study including your samples will still be used according to applicable laws

The Investigator must also contact the IRT to register the patient's discontinuation from study treatment.

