2.5.4 Supportive analyses

Sensitivity Analysis 1: A responder analysis of patients achieving a reduction of at least 1 in the Nasal Polyp score would be performed using a logistic regression, including covariates for treatment, visits and interaction between treatment and visit.

If the data suggests a logistic regression model is not the most appropriate for a responder analysis (*possible reasons may include majority of a particular response*) we will use additional analysis methods such as Cochran Mantel Haeszel test for the relative proportion of responders in each treatment arm and check whether there is a significant difference among them.

Sensitivity Analysis 2: The primary efficacy endpoint will be evaluated using the MMRM approach after imputing the Nasal Polyp Scores following surgery, only for patients who are considered as study withdrawals due to undergoing surgical procedures, by using the last observation carried forward (LOCF) technique. All other missing values will be imputed under the MAR approach within the MMRM model.

Sensitivity Analysis 3: The primary efficacy endpoint will be evaluated using the MMRM approach after imputing the Nasal Polyp Scores following surgery only for patients who are considered as study withdrawals due to undergoing surgical procedures, by using the worst observed score for that patient. All other missing values will be imputed under the MAR approach within the MMRM model.

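### Nothing keeps an NPS taken after nasal surgery out of the primary MMRM, and the SAP's visit-remapping rule permits one to stand as the Week 8 or Week 16 value

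*SAP*

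**What the plan says.** **Remapping.** Under SAP 2.1.3.10, data from a treatment or study discontinuation visit "may be used as the data from the scheduled visit" when the scheduled visit was missed and the discontinuation visit "occurred closer to the planned study day of the missing scheduled visit than to the planned study day of any other scheduled visit". Once remapped, the visit "will be treated as the scheduled visit for the purpose of all analyses so that no missing data imputation will be necessary". Surgery is not mentioned.

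**Surgery and the discontinuation visit.** Protocol 9.1.1 lists this among the events that require treatment to be discontinued: "If a patient undergoes nasal surgery, including but not limited to the following: treatment of nasal polyposis". Protocol 8 asks patients who leave the study early to attend a visit as soon as possible, "at which time all of the assessments listed for the final visit will be performed". In Table 8-1 the column headed EOT or TD includes nasal endoscopy.

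**Patients who only stop treatment.** Protocol 9.1.1 says they "should NOT be considered withdrawn from the study UNLESS they withdraw their consent" and that, where possible, "they should return for the assessments indicated" in the schedule.

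**Missing data.** SAP 2.5.3 handles missing values under MAR and does not say whether an observed post-surgery NPS is used. The model code in SAP 5.4.1 selects by visit number only. Sensitivity Analyses 2 and 3 in SAP 2.5.4 rerun the model after "imputing the Nasal Polyp Scores following surgery, only for patients who are considered as study withdrawals due to undergoing surgical procedures", by LOCF or by the patient's worst observed score. Every other missing score is left to MAR.

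**The concern.** Undergoing surgery is what triggers discontinuation, so an endoscopy prompted by it normally follows the operation. If the polyps were operated on, the reading reflects the surgeon's work and not the study drug. An operation for polyps suggests that medical treatment was not enough, yet it could supply some of the most favourable scores in the primary endpoint.

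The plan is also inconsistent with itself. By imputing scores after surgery and leaving the *other* missing scores to MAR, SAP 2.5.4 implies that its authors regard post-surgery scores as missing. SAP 2.1.3.10 can make some of them observed, with no imputation needed. A second route needs no remapping at all: an operated patient who stays in the study and attends Week 16 as scheduled contributes a post-surgery NPS directly. Two programmers could follow the text and obtain different primary results.

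**Working it through.** **1. The plan's sample size.** Inputs from SAP 3: difference 1.5, SD 1.8, one-sided alpha 0.0125, power 80%, dropout 10%.

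n = 2 × (1.8/1.5)² × (2.241 + 0.842)² = 27.4, so 28 evaluable patients per arm. Then 28 × 1.10 = 30.8, so 31 per arm and 93 in total, which matches the plan. At 28 per arm, power for one dose is 81% by the normal approximation and 79% by the t test.

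**2. Which discontinuation visits reach the primary model.** Table 8-1 plans visits on Days 28, 56, 84, 112 and 124 (follow-up call). The midpoints are 42, 70, 98 and 118.

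| Discontinuation visit | Nearest visit | NPS visit? |
|---|---|---|
| Days 15-41 | Week 4 | no |
| Days 43-69 | Week 8 | yes |
| Days 71-97 | Week 12 | no |
| Days 99-117 (Day 99 onward if the follow-up call is not counted) | Week 16 | yes |

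Days 42, 70 and 98 are ties, for which there is no rule. Within the 112 treatment days, Week 8 captures 27 days (24%) and Week 16 captures 14 days (12.5%).

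*Example with assumed values:* baseline NPS 6, surgery on Day 100, discontinuation visit on Day 104 with NPS 1. Day 104 is 8 days from Day 112 and 20 days from Days 84 and 124. If the rule is applied, the Week 16 change is -5.

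**3. Effect of one Week 16 value.** The FAS requires a baseline NPS of at least 4 on a scale of 0 to 8. Assume a post-surgery NPS of 0 to 2. The change then lies between 2 - 4 = -2 and 0 - 8 = -8. Relative to no change, one patient moves a 28-patient arm mean by 2/28 = 0.07 to 8/28 = 0.29 points. Divided by 1.5, that is 5% to 19% of the planned difference.

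**4. Illustrative worst case for power.** Simulated trials (100,000 per scenario), 28 per arm, SD 1.8, mean change 0 on placebo and -1.5 on active, t test at one-sided 0.0125. In k placebo patients the Week 16 change is replaced by a fixed post-surgery change, with none replaced on active. Cells show mean difference and power.

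| k on placebo | change -2 | change -4 | change -6 |
|---|---|---|---|
| 0 | 1.50, 79% | 1.50, 79% | 1.50, 79% |
| 1 | 1.43, 75% | 1.36, 67% | 1.29, 57% |
| 2 | 1.36, 70% | 1.22, 53% | 1.07, 33% |
| 3 | 1.29, 65% | 1.07, 38% | 0.86, 14% |

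With no true effect and three such patients on one active arm only, the 1.25% test rejects in 3.4%, 5.7% and 7.6% of trials.

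**5. How many patients remapping alone might bring.** A 10% dropout is about 3 patients per arm. If all 3 left because of surgery, with visits spread evenly over treatment, 3 × 14/112 = 0.4 per arm would map to Week 16. That shifts the arm mean by about 0.03 (0.375 × 2/28) to 0.11 (0.375 × 8/28) points. Operated patients who stay and attend Week 16 come on top of this and are not limited by the dropout rate.

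**The case against.** The strongest reply is that the rule is narrow and optional. It says that the data may be used, it needs a missed visit, and only two windows feed the primary model. Patients who stop treatment are asked to stay in the study, and for those who withdraw consent Protocol 9.1.2 treats later data as missing. All of this limits the number affected, but it does not close the gap. An unstated choice over primary-endpoint data is itself a weakness, Protocol 9.1.2 also asks for a final evaluation, and patients who stay in reach Week 16 without remapping.

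Four stronger readings are tempting, and the documents do not support them:

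- *Every operated patient is scored as a near-maximal responder.* No post-operative NPS is given, and the surgery list in Protocol 9.1.1 includes procedures, such as septal correction, that need not remove polyps.
- *Sensitivity Analysis 2 carries a post-surgery score forward.* On the ordinary reading, a score following surgery is what that analysis replaces, not its source. The wording merely fails to say that the last observation must precede surgery.
- *Sensitivity Analysis 3 is contaminated too.* A higher NPS is worse, so a low post-surgery reading would not be the worst score.
- *The power losses in the table are to be expected.* They put every operated patient at Week 16 on one arm. That fits poorly with a 12.5% window and 10% dropout if remapping is the only route. A remapped Week 8 value affects Week 16 only through the within-patient correlation, which was not simulated. The 28 patients are also already net of dropout, although using 29 changes little (8/29 = 0.28).

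A last objection stands in full: setting observed post-surgery scores to missing is a choice of estimand in a plan that invokes intention to treat, and MAR is questionable for treatment failures.

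**Conclusion.** The gap is real. The plan permits a post-surgery discontinuation endoscopy to become the Week 8 or Week 16 NPS, nothing excludes a scheduled post-surgery NPS, and both sit badly with Sensitivity Analyses 2 and 3. Under an assumed post-surgery NPS of 0 to 2, one Week 16 value moves an arm mean by 5% to 19% of the planned difference. The direction depends on the arm: more surgery on placebo dilutes a true effect, and more on an active arm inflates the estimate.

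The total size is unknown because the documents give neither a surgery rate nor a post-operative NPS. It may be small, and the power table is an illustrative worst case. The per-patient figures use simple arm means in place of the MMRM and measure the shift from no change. The point is worth settling before unblinding because it concerns the primary endpoint and costs little.

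**What to change.** - **SAP 2.1.3.10 and 2.5.3:** state that an NPS obtained after nasal surgery, whether at a remapped or a scheduled visit, is not used as observed data in the primary MMRM and is treated as missing from the date of surgery.
- **SAP 2.5.4, Sensitivity Analysis 2:** state that LOCF uses the last endoscopy before surgery. Sensitivity Analyses 2 and 3 should then cover every operated patient whose scores are set to missing, including those who stay in the study.
- **Reporting:** list the excluded readings by arm with the surgery date.

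The cost is a few sentences and one flag on surgery date; Protocol 6.2.1 already requires procedures to be recorded on the CRF. The downside is that a few observed values are dropped and the primary estimand becomes hypothetical for surgery under MAR. The SAP should say so and present Sensitivity Analyses 2 and 3 as the test of that assumption. No clinical rule changes.

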2.1.3.11 Last contact date

The maximum of the date of last visit, date of last epoch completion, date of withdrawal of consent would be the date of last contact for the patient participating in the study.

The last contact date is defined as the latest complete date from the above list or the cut-off date whichever comes first. The cut-off date will not be used for last contact date, unless the patient was seen or contacted on that date. No date post cut-off date will be used. Completely

imputed dates (e.g. the analysis cut-off date programmatically imputed to replace the missing end date of a dose administration record) will not be used to derive the last contact date.

2.2 Analysis sets

The **Screened Set (SCR)** will consist of all patients who provided informed consent

The **Full Analysis Set (FAS)** will be comprised of all randomized patients who meet both of the following criteria:

- Received at least one dose of study treatment
- Have a baseline NPS score ≥ 4 as measured by the central reader.

According to the intent to treat principle, subjects will be analyzed according to the treatment they have been assigned to at the randomization. However, if patients received study treatment without being randomized into the study they will be excluded from the FAS.

The **Safety Set (SAF)** includes all subjects who received at least one dose of study treatment. Subjects will be analyzed according to the study treatment received, where treatment received is defined as the randomized/assigned treatment if the patient took at least one dose of that treatment or if the patient received more than one treatment, then the patient would be analyzed according to the randomized treatment.

The analysis of the primary objectives will be performed on the FAS. The FAS will be used for the analysis of all other efficacy variables. The SAF will be used in the analysis of all safety variables.

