### **12.1 Analysis sets**

[figure not shown]
The Full Analysis Set (FAS) will be comprised of all randomized patients who meet both of the following criteria:

- Received at least one dose of study treatment
- Have a baseline NPS score  $\geq 4$  as measured by the central reader.

According to the intent to treat principle, subjects will be analyzed according to the treatment they have been assigned to at the randomization. However, if patients received study treatment without being randomized into the study they will be excluded from the FAS.

The Safety Analysis Set (SAF) includes all subjects who received at least one dose of study treatment. Subjects will be analyzed according to the study treatment received, where treatment received is defined as the randomized/assigned treatment if the patient took at least one dose of that treatment or the first treatment received if the randomized/assigned treatment was never received.

The analysis of the primary objectives will be performed on the FAS. The FAS will be used for the analysis of all other efficacy variables. The SAF will be used in the analysis of all safety variables.

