2.4.1.1 Duration of exposure

Duration of exposure to a study drug will be calculated as the number of days between the first dose date and the last dose date exposed to that treatment over the specified period (expressed as: Duration of exposure (weeks) = (Date of last known dose of study drug – Date of first dose of study drug + 1)/7).

In addition, the duration of exposure will be summarized as a categorical variable classified into ≤ 4 weeks, > 4 – 8 weeks, > 8 – 12 weeks and > 12 weeks.

Dose administration data will be listed for patients in the SAF.

Patients in the randomized set who received any wrong study medications will be listed. These patients will be identified using the information recorded on the DAR page of the eCRF. If there is a record with reason = dispensing error, then the pack number will be used to identify whether or not the patient received the wrong study drug.

The number of patients with dose adjustments (interruption, or permanent discontinuation) and the corresponding reasons will be summarized for the study treatment.

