2.14 Interim analysis

No interim analysis is planned.

3 Sample size calculation

Based on clinical judgement a mean reduction of 1.5 in polyp score (as measured by the NPS) can be expected with fevipiprant (450 mg and 150 mg) and SoC as compared to Placebo and SoC. Considering this factor, the sample size was calculated under an 80% power and 1.25% one sided alpha for comparison of each of the two dose levels of fevipiprant and SoC with placebo and SoC. A 10% dropout rate is considered as appropriate with reference to prior studies (omalizumab study by Gevaert et al 2013 and dupilumab study by Bachert et al 2016). From prior literature standard deviation of 1.8 is considered as appropriate for the change of score from baseline at 16 weeks in Nasal Polyp Score.

The sample size calculation was performed using the software PASS 2008 using inequality tests using difference of two independent means with equal variance.

The randomization will be performed in a 1:1:1 ratio for the two separate doses level of fevipiprant (450 mg and 150 mg) and the placebo arm. Under these assumptions (effect size = 1.5, equal SD = 1.8, power = 80% for each arm individually, one-sided alpha = 0.0125 and dropout = 10%), the total sample size yielded was 93 with 31 patients in each arm. The sample size provides a power of 80% for each comparison but since we will be testing correlated hypothesis using a Dunnett's test, this is a lower bound on the power. The real power is expected to be higher if in at least one of the 2 dosages i.e. fevipiprant 150 mg or fevipiprant 450 mg, the standardized effect size (in other words, keeping the assumption of an SD of 1.8 in each group) is equal to the clinically significant value of 1.5 and there is some treatment benefit in the other groups as well. However, if the effect size is equal to 1.5 in both of the groups, the power will be substantially higher i.e. around 93%.

4 Change to protocol specified analyses

Not Applicable

5 Appendix

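### SAP 2.2 drops the protocol's fallback for patients who never took their randomized treatment, leaving the safety-set arm undefined or wrong in rare cases, and the SAP declares no change (minor)

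*SAP*

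**What the plan says.** Protocol 12.1 defines the safety-set arm in two steps. In the first, "treatment received is defined as the randomized/assigned treatment if the patient took at least one dose of that treatment". The second covers everyone else: "the first treatment received if the randomized/assigned treatment was never received".

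SAP 2.2 opens its safety-set paragraph with the same principle, "Subjects will be analyzed according to the study treatment received", and repeats the first step. The second step is missing. In its place, joined by an *or*, stands "if the patient received more than one treatment, then the patient would be analyzed according to the randomized treatment". That clause does not require that any dose of the randomized treatment was taken.

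Three other places in the SAP bear on this:

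- SAP 2.2 on the scope of the set: "The SAF will be used in the analysis of all safety variables".
- SAP section 4, headed "Change to protocol specified analyses", is marked as not applicable.
- SAP 2.4.1.1 foresees dispensing errors, to be identified from dose administration records and pack numbers: "Patients in the randomized set who received any wrong study medications will be listed". It does not say which arm those patients are summarized under.

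**The concern.** A treatment-received rule has to give every treated patient exactly one arm, and that arm should be one whose treatment the patient took. The protocol's rule does both. The SAP's wording, taken as it stands, can fail on each count, and nothing in the SAP tells the reader that the rule has moved.

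The situation is foreseeable, even if uncommon. The design is double-dummy, two bottles are dispensed at each of four visits (Protocol Table 8-1, SAP 2.4.1), and the SAP itself plans to look for wrong kits. The rule feeds every by-arm safety table. If such a patient turns up and the rule gives no answer, someone has to decide the arm at programming time, possibly after unblinding.

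**Working it through.** No stated figure is in dispute, so the check is to apply both rules to every possible case.

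**Inputs.** Three arms (Protocol 6.1.3); the two rules as worded in Protocol 12.1 and SAP 2.2; 31 patients per arm (Protocol 12.8.1, SAP section 3).

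**Rules as coded.**

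- Protocol: randomized arm if that treatment was ever taken; otherwise the first treatment taken.
- SAP, literal: randomized arm if that treatment was ever taken; randomized arm if more than one treatment was taken; otherwise nothing is stated.

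**Cases.** The ordered sequences of distinct treatments a patient could take number 3 (one treatment) + 6 (two) + 6 (three) = 15. Over three randomized arms this gives 3 × 15 = 45. A treatment here means one of the three randomized regimens.

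**Result for a patient randomized to placebo.**

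| Treatments taken, in order | Protocol 12.1 | SAP 2.2, literal |
|---|---|---|
| Any sequence that includes placebo (11 of 15) | Placebo | Placebo |
| 150 mg only | 150 mg | not defined |
| 450 mg only | 450 mg | not defined |
| 150 mg, then 450 mg | 150 mg | Placebo |
| 450 mg, then 150 mg | 450 mg | Placebo |

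The other two arms give the same pattern. Overall, 3 × 11 = 33 cases agree, 3 × 2 = 6 are undefined under the SAP, and 3 × 2 = 6 give a different arm. These count possible sequences and are not expected frequencies.

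**Direction of the six differing cases.** Compared with the protocol rule:

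- 2 move a patient from active to placebo (randomized to placebo, both active doses taken).
- 2 move a patient from placebo to active (randomized to one active dose, placebo taken first and then the other dose).
- 2 move a patient from one active dose to the other (randomized to one active dose, the other dose taken first and then placebo).

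No single direction of error follows from the clause.

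**Size per patient.** 1/31 = 0.032, or about 3.2 percentage points of an arm's incidence for one affected patient who had the event. This is approximate, because arm denominators also shift by one.

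**With the protocol fallback restored.** All 45 sequences receive an arm, and in each the patient took that arm's treatment at least once.

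**The case against.** The strongest reply is that the SAP clause is a drafting slip. It can be read as covering the ordinary mix-up, where a patient took the randomized treatment plus another. On that reading it only repeats the first step and gives the protocol's answer. SAP section 1 also says the SAP implements protocol section 12, so where the SAP is silent the protocol can fill the gap, and the SAP's own lead sentence points the same way. Kits are assigned by medication number through the IRT, so taking two different wrong treatments and never the right one would need repeated errors. Finally, the safety summaries are descriptive, and patients given wrong medication are listed individually.

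Most of this stands, and it is why the point is minor. It does not remove the point. If the clause is redundant, the fallback has still been lost. For a patient with two wrong treatments the SAP is not silent: it states an arm, and that arm conflicts with its lead sentence. A listing makes such a patient visible but does not settle the column of the summary tables.

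A reader might go further and infer that the SAP's wording shifts active-dose events into the placebo column and so biases the safety comparison towards no difference. The documents do not support that. Only two of the six differing sequences go in that direction, all six are remote, and the protocol's own rule keeps a placebo patient under placebo after a single placebo dose, whatever else was taken. For a wrong kit at a later visit, after correct dosing, the two rules give the same arm.

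**Conclusion.** Wrong as written, minor. SAP 2.2 does not reproduce the protocol's treatment-received rule, and section 4 does not declare the difference. Read literally, it gives no arm to a patient who took one wrong treatment only, and an arm never taken to a patient who took both non-assigned treatments. The first gap is the more likely to arise.

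The documents give no dispensing-error rate, so the number of affected patients is unknown. A figure close to zero among 93 patients is a judgement. The 3.2-point figure assumes the planned 31 per arm and a patient who had the event in question. The conclusion rests on the literal wording; nothing in the documents shows that the change was intended. It would also be wrong to infer that restoring the protocol rule clears the placebo column of active-dose events, since both rules keep a patient in the randomized arm after one assigned dose.

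**What to change.** In SAP 2.2, replace the clause on more than one treatment with the protocol 12.1 fallback: randomized treatment if at least one dose of it was taken, otherwise the first treatment received. State that this is derived from the pack numbers and dose administration records already named in SAP 2.4.1.1. If the sponsor does intend a different rule, it should cover the patient who took a single wrong treatment, and be declared and justified in SAP section 4.

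The cost is one sentence, with no new data, and it should be done before unblinding.
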